3.3.1.4 Time to Clinical Worsening

Time to clinical worsening will be evaluated as an exploratory endpoint from the time of randomization until 1 of the following criteria are met:

- a. Hospitalization due to a cardiopulmonary indication
- b. Decrease in 6MWD > 15% from Baseline directly related to disease under study, at 2 consecutive visits and at least 24 hours apart
- c. Death (all causes)
- d. Lung transplantation

Because there are no Food and Drug Administration (FDA) approved therapies for the treatment of WHO Group 3 PH, subjects experiencing clinical worsening may remain on study therapy for the duration of the study (or until criteria for study termination are met per Section 8.1 of the protocol). However, if a subject is removed from study therapy due to clinical worsening, the subject must return to the clinic for regularly scheduled study visits (excluding the Week 15 Visit) to be eligible for the open-label extension study (Section 7.8). Subjects experiencing death or lung transplantation will be discontinued from the study per Section 8.1 of the protocol.

3.3.1.5 Change in Distance Saturation Product

Change in DSP is the product of distance walked and lowest SpO₂ recorded during the 6MWT. This assessment has been shown to be predictive of mortality in patients with idiopathic pulmonary fibrosis and as such will be evaluated as an exploratory endpoint in this study (Lettieri 2006). Change from Baseline to Week 16 or ET in DSP will be calculated.

3.3.1.6 Optional Biomarker

For subjects consenting to the optional biomarker sample, blood will be collected for the evaluation of biomarkers (specific targets to be determined) at Baseline and at Week 16 or ET.

3.3.1.7 Optional Whole Genome Sequencing

For subjects consenting to whole genome sequence analysis, a blood sample will be collected at Baseline. These samples will be shipped to the central laboratory for processing and storage prior to analysis. Whole genome sequences will be analyzed for genetic makers that may be associated with clinical response and tolerability.

3.3.2 Safety

During this study, treatment emergent changes in PE findings, vital signs, clinical laboratory parameters, ECG parameters, PFTs, oxygenation, and the development of AEs after treatment will be the primary assessments of safety. Hospitalizations due to cardiopulmonary indications will also be recorded from the time of informed consent until study termination (or ET for those subjects discontinuing the study prematurely). Exacerbations of underlying lung disease will also be recorded from the time of informed consent until study termination.

3.3.2.1 Medical History and Physical Examinations

A complete medical history, demographics, PH history, and PE will be conducted during Screening. If any changes to the medical history occur between the Screening and Baseline Visit, those should be recorded. Significant past or present illnesses, current prescription or nonprescription medications (including vitamins and herbal products), and history of allergies or idiosyncratic responses to drugs should be recorded. Any significant changes to the subject's medical condition and PE must be documented throughout the course of the study. A complete PE will also be conducted by appropriate study personnel (as documented on the Delegation of Authority Log) at the Week 16 or ET Visit. Any clinically significant changes from Baseline noted during the Week 16 or ET PE should be reported as AEs.

3.3.2.2 Vital Signs

Vital signs will be assessed at Screening, Baseline, and each subsequent study visit or ET.

Vital signs measured will include blood pressure (systolic and diastolic), HR, respiratory rate

(RR), temperature, and weight. Height will be assessed at Screening only. Vital signs must be assessed following at least 5 minutes of rest (sitting) to ensure accurate measurement. No other measurements or procedures should be performed during this 5-minute period. When possible, vital signs should be collected prior to the 6MWT. If vital signs cannot be obtained prior to the 6MWT, they should be obtained after recovery of the 6MWT. Vital signs should also be assessed in the case of abnormal clinical signs and symptoms.

3.3.2.3 12-Lead Electrocardiogram

A 12-lead ECG will be recorded after at least 5 minutes of rest in the semi-recumbent position at Baseline (prior to study drug) and repeated at the Week 16 or ET Visit. Recordings should include lead II as a rhythm strip and contain at least 5 QRS complexes. ECG parameters to be collected include rhythm, HR, PR interval, QT interval, QRS duration, and any clinically significant abnormalities.

3.3.2.4 Clinical Laboratory Assessments

The results of all clinical laboratory tests conducted at Screening and Baseline must be assessed by the Investigator to determine each subject's eligibility to participate in the study prior to starting study drug. Screening and Baseline clinical laboratory assessments can be combined into a single blood draw if all eligibility criteria are met within 48 hours prior to the first dose of study drug at Baseline. Central laboratory data are ultimately used to qualify subjects for the study. However, for subjects who are well known to the Investigator and who are clinically stable, the Investigator may confirm eligibility using local laboratory values so as not to delay randomization while waiting for central laboratory results if the Screening and Baseline Visits are combined.

Clinical laboratory results outside the normal reference range must be assessed for clinical significance by the Investigator. Clinically significant refers to a laboratory value that is unusual with respect to the subject's medical history or current health status.

Clinically significant abnormal laboratory test values will be reported as AEs and treated and/or followed-up until the symptoms or values return to normal or acceptable levels, as judged by the Investigator. Where appropriate, medical tests and examinations will be performed to assess and document resolution.

3.3.2.4.1 Clinical Chemistry and Hematology

Blood for the measurement and evaluation of clinical chemistry and hematology, will be collected at the Screening and Baseline Visits prior to administration of study drug and repeated at Week 8 and Week 16 or ET to assess for treatment-emergent changes in clinical chemistry and hematological laboratory parameters. Values for the following parameters will be obtained:

Electrolyte Panel Chemistry Panel Hematology Panel Sodium Total bilirubin Hemoglobin Potassium Alkaline phosphatase Hematocrit Bicarbonate Alanine aminotransferase Red blood cell count Chloride Aspartate aminotransferase • Red blood cell morphology Urea nitrogen White blood cell count Creatinine Platelet count Calcium Albumin

3.3.2.4.2 Pregnancy Testing

Females of childbearing potential will undergo a urine pregnancy test at Screening followed by urine pregnancy tests at Baseline and each subsequent study visit (or Baseline Visit if the Screening and Baseline Visits are combined) or ET. A positive pregnancy test will exclude the subject from further participation in the study. Pregnant subjects who are discontinued from the study will be transitioned to an alternate therapy at the discretion of the Investigator.

3.3.2.5 Pulmonary Function Tests

Pulmonary Function Tests will be assessed at Baseline and repeated at Week 8 and Week 16 or ET. Baseline PFTs are to be conducted prior to randomization and after recovery from the 6MWT. The Week 8 and Week 16 or ET PFTs should be conducted after recovery from the 6MWT. If the PFTs are done both prior to and after a bronchodilator, only the prebronchodilator values will be recorded.

The following parameters will be recorded (absolute values and % predicted): FEV1, FVC, TLC, and DLCO (uncorrected for hemoglobin and lung volume).

3.3.2.6 Oxygenation

3.3.2.6.1 Pulse Oximetry

Pulse oximetry will be assessed immediately prior to, throughout the conduct of, and immediately after each scheduled 6MWT assessment at Baseline, Week 4, Week 8, Week 12, Week 15, and Week 16 or ET. Pulse oximetry will also be performed at Screening during the practice 6MWT assessment as applicable. Pulse oximetry will include the collection of SpO₂ and HR. The SpO₂ and HR obtained immediately prior to and immediately following completion of the 6MWT will be recorded in the electronic case report form (eCRF). In addition, the lowest recorded SpO₂ obtained during each 6MWT will be recorded in the eCRF.

When possible, pulse oximetry should be recorded using the provided pulse oximeter (Nonin 3150). In the event the provided pulse oximeter cannot be used (ie, subject has known issues with obtaining accurate readings from a finger probe, etc) an alternative device may be used with prior Sponsor approval so long as the same device is used for all planned 6MWT.

3.3.2.6.2 Supplemental Oxygen Requirement

The amount of supplemental oxygen (L/min) required at rest will be assessed at Baseline and at regularly scheduled visits or ET. The amount of supplemental oxygen required at the 6MWT assessment will also be recorded for each 6MWT assessment.

3.3.2.7 Adverse Events

Adverse events will be recorded throughout the course of the study from the time that each subject signs the ICF until the time screen failure is documented, or until the subject is either discontinued from the study or all Week 16 study assessments have been completed. Each subject will be questioned for AEs at each scheduled study visit and during required telephone/email contacts. Subjects will also be instructed to spontaneously report all AEs throughout the study.

All AEs should be followed until either resolution (or return to normal or baseline values), until they are judged by the Investigator to no longer be clinically significant, or for at least 30 days if the AE extends beyond the final study visit. All AEs meeting the criteria for serious (ie, serious adverse events [SAEs]) should be followed until resolution, death, or the

subject is lost to follow-up even if they are ongoing more than 30 days after completion of the final study visit (Week 16 or ET). All AEs/SAEs that occur while the subject is in study will be recorded as instructed in this protocol.

Sections 9 and 15.2 provide the guidelines and definitions for recording AEs.

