- All AEs will be documented from the time of informed consent until the time screen failure is documented, or until the subject is either discontinued from the study or all Week 16 study assessments have been completed and should be followed until either resolution (or return to normal or base line values), until they are judged by the Investigator to no longer be clinically significant, or for at least 30 days if the AE extends beyond the final study visit (Week 16).
- On Hospitalizations due to cardiopulmonary indications must be recorded in the eCRF from the time of informed consent until study termination. Adverse events resulting in hospitalizations, regardless of cause or duration, should also be recorded as SAEs per Appendix 15.2.
- P Exacerbations of underlying lung disease; defined as an acute, clinically significant, respiratory deterioration characterized by evidence of new widespread alveolar abnormality (see Section 3.3.2.10). Exacerbations will also be recorded as AEs or SAEs per Appendix 15.2.
- ^q Time to clinical worsening will be measured from the time of randomization until 1 of the following criteria are met: hospitalization due to a cardiopulmonary indication; decrease in 6MWD > 15% from Baseline directly related to the disease under study, at 2 consecutive visits and at least 24 hours apart; death (all causes); or lung transplantation.
- ^r Once all entry criteria have been met and the randomized treatment assignment confirmed, the first dose of study drug (3 breaths; 18 mcg) will be inhaled in the clinic, followed by at least a 1 hour observation period (Defined as Day 1).
- Subjects who permanently discontinue study drug during the 16-week Treatment Phase are encouraged to undergo premature termination assessments prior to discontinuing study drug and are required complete all remaining scheduled study visits through Week 16 (excluding the Week 15 Visit) to be eligible for entry into the open-label study.
- ^t The premature termination of study drug visit should be conducted prior to study drug discontinuation or as close as possible to the last dose of study drug.

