4.1 INCLUSION CRITERIA

- 1. Subject voluntarily gives informed consent to participate in the study.
- 2. Males and females aged 18 years or older at the time of informed consent.
 - a. Females of reproductive potential¹ must be non-pregnant (as confirmed by a urine pregnancy test at screening) and non-lactating, and will:
 - i. Either abstain from intercourse (when it is in line with their preferred and usual lifestyle), or
 - ii. Use 2 medically acceptable, highly-effective forms of contraception² for the duration of study, and at least 30 days after discontinuing study drug.
 - b. Males with a partner of childbearing potential must use a condom for the duration of treatment and for at least 48 hours after discontinuing study drug.
- 3. The subject has a confirmed diagnosis of WHO Group 3 PH based on CT imaging, which demonstrates evidence of diffuse parenchymal lung disease performed within 6 months prior to randomization. Subjects may have any form of ILD or CPFE.
- 4. Subjects are required to have a RHC within 1 year prior to randomization with the following documented parameters:
 - a. Pulmonary vascular resistance (PVR) > 3 Wood Units (WU) and
 - b. A pulmonary capillary wedge pressure (PCWP) of \leq 15 mmHg and
 - c. A mean pulmonary arterial pressure (mPAP) of \geq 25 mmHg
- 5. Baseline 6MWD \geq 100 meters.
- 6. Subjects on a chronic medication for underlying lung disease (ie, pirfenidone, nintedanib, etc) must be on a stable and optimized dose for ≥ 30 days prior to randomization.
- 7. In the opinion of the Investigator, the subject is able to communicate effectively with study personnel, and is considered reliable, willing and likely to be cooperative with protocol requirements, including attending all study visits.
- 8. Subjects with connective tissue disease (CTD) must have a Baseline FVC of < 70%.

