9.1.2 Serious Adverse Event

A SAE is an AE occurring at any time after informed consent that results in any of the following outcomes:

- Death
- A life-threatening AE
- Inpatient hospitalization or prolongation of existing hospitalization
- A persistent or significant disability/incapacity
- A congenital anomaly/birth defect
- Results in a medically important event of reaction

Life-threatening in this context refers to a reaction in which the subject was at risk of death at the time of the reaction; it does not refer to a reaction that hypothetically might have caused death if more severe.

Medical and scientific judgment should be exercised in deciding whether other situations should be considered serious reactions, such as important medical events that might not be immediately life-threatening or result in death or hospitalization, but might jeopardize the subject or might require intervention to prevent 1 of the other outcomes listed above.

Examples of such events are intensive treatment in an emergency room or at home for allergic bronchospasm, blood dyscrasias, or convulsions that do not result in hospitalization or development of dependency or abuse. Any suspected transmission via a medicinal product of an infectious agent is also considered a serious adverse reaction.

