9.3 FOLLOW-UP OF ADVERSE EVENTS

All AEs should be followed until either resolution (or return to normal or baseline values), until they are judged by the Investigator to no longer be clinically significant, or for at least 30 days if the AE extends beyond the final visit. All SAEs that occur during the study will be followed until resolution, death, or the subject is lost to follow-up even if they are ongoing more than 4 weeks after completion of the final study visit. Supplemental measurements and/or evaluations may be necessary to investigate fully the nature and/or causality of an AE or SAE. This may include additional laboratory tests, diagnostic procedures, or consultation with other healthcare professionals. The eCRF pages should be updated with any new or additional information as appropriate.

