9.5 PREGNANCY

If a study subject becomes pregnant during participation in this clinical study, site staff must notify the Sponsor within 24 hours of learning of the pregnancy by completing the Pregnancy Notification Form and submitting via fax or email to Global Drug Safety at United Therapeutics Corporation

The United Therapeutics Global Drug Safety department will follow-up with the Investigator to ensure appropriate data are provided regarding the outcome of the pregnancy, and to ask the Investigator to update the Pregnancy Notification Form. Pregnancy only becomes an AE/SAE if there is an abnormal outcome, a spontaneous abortion, an elective termination for medical reasons, or a congenital anomaly in the offspring.

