#### **12.2 ADVERSE EVENTS**

All AEs will be coded to the appropriate PT and SOC using MedDRA. AEs will be listed by treatment group including all details recorded on the eCRF plus an indicator of whether the event was treatment-emergent. The AE listings will include the AE verbatim term and its corresponding PT and SOC.

The AE summaries will be limited to include only treatment-emergent AEs. Treatmentemergent AEs are those AEs with onset date equal to or after the start date of the study drug. The non-treatment-emergent AEs (the AEs occur after signing the informed consent form but before receiving study drug) will be listed but not included in summary tables.

All summaries will include the number and percentage of subjects experiencing each type of adverse event and the total number of each type of adverse event, in order of overall frequency and/or SOC. Serious adverse events (SAE) and non-serious AEs will also be summarized by SOC and PT.

The total number of AEs and the AE rates will be calculated and summarized for each display, as appropriate. The AE rate will be calculated as the total number of AEs divided by the total patient years of exposure to study drug per treatment group.

Adverse events possibly or probably related to study drug will be summarized. An AE summary by severity (mild, moderate, and severe) will also be provided.

Separate listings and summary tables will be provided for all SAEs, AEs leading to the discontinuation of study drug, and all deaths during the study (if data permit). For listing of deaths, information for all subjects who die during the study period from the randomization to the end of study (including 30 days after the last study treatment dosing) will be included.

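### The SAP lists deaths to 30 days after the last dose, but the protocol plans no collection of new deaths or SAEs after Week 16 or study exit

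*Protocol*

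**What the plan says.** **Recording of new events.** Protocol 3.3.2.7 and the AE footnote to the schedule in 3.2 run from consent "until the subject is either discontinued from the study or all Week 16 study assessments have been completed". Sections 3.3.2.9 and 3.3.2.10 stop recording hospitalizations and exacerbations at study termination. Section 3.6 describes participation as 4 weeks of screening plus 16 weeks of treatment. The schedule has no visit or call after Week 16, and the weekly-contact row is empty in the early-termination column.

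**Dosing at the end of the study.** Section 7.6 places the Week 16 peak walk 10 to 60 minutes after a dose, so a completer takes study drug on the day recording closes.

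**Follow-up of open events.** Section 3.3.2.7 follows AEs to resolution, until no longer clinically significant, "or for at least 30 days if the AE extends beyond the final study visit". Section 9.3 adds: "All SAEs that occur during the study will be followed until resolution, death, or the subject is lost to follow-up". Section 8.1 has a similar rule for subjects who stop drug because of an AE, and encourages anyone who stops drug to attend the remaining visits to Week 16, except Week 15.

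**Reporting.** SAP 12.2 states that deaths "from the randomization to the end of study (including 30 days after the last study treatment dosing) will be included" in the death listing. It does not say what happens to this window when a subject starts open-label drug. The SAP's treatment-emergent AE definition has a start but no end.

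**The concern.** A listing defined to 30 days after the last dose reads as a complete account of deaths in that period. If nobody is asked about vital status after Week 16 or study exit, it will instead hold three kinds of information under one heading: deaths systematically recorded up to exit, fatal outcomes of SAEs already open at exit, and whatever else a site happens to hear and report.

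The gap bears on subjects of safety interest. Section 7.8 bars those who stop drug for treatment-related AEs from the extension even if they attend every remaining visit, so the prospect of open-label drug gives them no reason to stay. Section 8.2 closes a lost subject's record at the last contact and describes no vital-status check. If exit rates differ between arms, the incompleteness differs too.

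Subjects who roll over raise a separate problem. The 30 days after their last blinded dose may be spent on open-label treprostinil. Without a rule, a death in that period could be shown under the randomized arm of the blinded study, including placebo.

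**Working it through.** **Inputs.** Week 16 target Day 113, window ±5 days (protocol 3.2); death window of last dose + 30 days (SAP 12.2); 314 subjects and about 15% discontinuation (SAP 5). Randomization is taken as Day 1.

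The plan's own figure first: 266 / (1 − 0.15) = 312.9, rounded up to 313, or 314 for two equal arms. The planned total is reproduced. It does not bear on the mismatch, but it supplies the counts used below.

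**Step 1: completer, last dose on the Week 16 day, not entering the extension.**
- Recording of new events ends on Day 113.
- The SAP window ends on Day 113 + 30 = Day 143 (Day 138 to 148 across the visit window).
- Post-dose days open to new events: 0 of 30.
- Uncollected share of the SAP window: 30 / 143 = 21%.

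**Step 2: subject who stops drug on Day d but stays to a Week 16 visit on Day 113.** Post-dose days covered = min(30, 113 − d).
- All 30 days are covered if d ≤ 113 − 30 = 83 (78 to 88 across the visit window).
- If the last dose is on Day 100, 113 − 100 = 13 of 30 days are covered.

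**Step 3: subject who leaves the study on the day of the last dose, Day d.** New-event recording covers 0 of 30 days. The uncollected share is 30 / (d + 30); for d = 57 it is 30 / 87 = 34%. The 21% in Step 1 therefore does not carry over to early leavers.

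**Step 4: how many subjects.** 0.15 × 314 = 47 is an upper bound at the planned rate on those who leave the study early, because the 15% does not separate stopping drug from leaving the study. About 0.85 × 314 = 267 reach Week 16, but the number entering the extension is not given. The count affected is therefore unknown.

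**Step 5: possible number of deaths in the 30 days.** The documents give no mortality rate for this population. Assuming annual mortality r between 5% and 30%, expected deaths = N × [1 − (1 − r)^(30/365.25)].

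| N | r = 5% | r = 30% |
|---|---|---|
| 47 (all discontinuations are study exits) | 0.2 | 1.4 |
| 267 (no completer enters the extension) | 1.1 | 7.7 |

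Both rows are ceilings on what could be missed at a given r: open SAEs are followed to death, and extension entry shrinks the second row.

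**The case against.** The best case for the plan is that much of the 30 days is covered. Open AEs are followed, open SAEs have no time limit, and a fatal outcome of an open SAE is captured. A subject who stops drug for an AE is followed for that AE. Subjects withdrawn for clinical worsening must attend the remaining visits to stay eligible for the extension. Section 9.1.2 also sets only a start for SAEs ("A SAE is an AE occurring at any time after informed consent"), so a site that learns of a later death might report it. Safety data are summarized without inference, and no efficacy endpoint is touched.

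Most of this stands, and it rules out several stronger readings that a reader might infer:

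- *That the 30-day data are not collected at all.* Follow-up of open events and retention to Week 16 contradict this.
- *That recording can stop before the last dose because of the early-termination visit.* The schedule footnote says "The premature termination of study drug visit should be conducted prior to study drug discontinuation or as close as possible", but recording ends at study discontinuation, not at that visit, and further visits are expected after it. Only a subject who leaves the study at that visit while still on drug could be affected.
- *That the contraception period promises data.* The requirement of at least "30 days after discontinuing study drug" is a conduct rule. Section 9.5 ("If a study subject becomes pregnant during participation in this clinical study") does not contradict it.
- *That SAE counts fall short of a SAP target.* The 30-day window is stated for the death listing only.
- *That an open-label death will be listed under placebo.* The SAP is silent, the extension's documents are not available here, and SAP 9.1 lists last-dose dates and extension enrollment, from which such a death could be recognized.

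What does not stand is the reliance on the open-ended SAE definition. The opening of protocol Section 9 and 3.3.2.7 tie recording to the time the subject is in the study, and passive reporting is not ascertainment. A death from an event that was not open at exit has no planned route into the listing.

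**Conclusion.** The mismatch is real but narrow. The SAP commits to a death listing through 30 days after the last dose, and the protocol has no step that would find new deaths or SAEs in that period for subjects who leave early or who complete without rolling over. For a subject dosed to Day 113 the shortfall is 30 of 143 days (21%). The number of subjects affected cannot be stated, and the number of deaths at stake depends on an assumed mortality rate; a few deaths is plausible and none is possible. For extension entrants, attribution is undefined rather than wrong. Sample size and efficacy analyses are unaffected. This should be corrected because the change is cheap and the listing would otherwise look more complete than it is.

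**What to change.** - **Protocol 3.3.2.7 and the AE footnote in 3.2:** for subjects not entering RIN-PH-202, add one phone or email contact 30 days after the last blinded dose, asking for vital status and new SAEs.
- **SAP 12.2:** for subjects who enter the extension, end the death window at the first open-label dose. Show deaths after the end of blinded treatment separately from those on treatment.
- **Minimum alternative:** if no contact is added, limit the SAP death window to the period actually collected, so that the two documents agree.

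The cost is wording in both documents, one eCRF contact page, one more remote contact for subjects not rolling over, and a last-subject-out date up to 30 days later. The minimum alternative needs only the SAP wording, but leaves the post-treatment period unobserved.
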